7.7 Data collection

The following data will be collected from all patients:

Randomisation data

- Checklist to ensure the patient meets the eligibility criteria
- ASA grade
- Planned surgical procedure category
- Planned level of care on the first night after surgery (Appendix 1)
- Trial patient identifier (generated automatically at point of randomisation)

Baseline data

- Diagnosis of chronic lung disease (COPD, asthma, interstitial lung disease)
- Diagnosis of ischaemic heart disease
- Diagnosis of diabetes mellitus
- Diagnosis of heart failure
- Diagnosis of liver cirrhosis

- Diagnosis of active cancer (indication for surgery Y/N)
- Diagnosis of previous stroke or transient ischaemic attack
- Current smoker (smoked within last 14 days)
- Preoperative immunosuppressant therapy within 30 days before surgery
- SARS-CoV-2 test before surgery
- Ethnicity (to calculate estimated glomerular filtration rate)
- Gender
- Age
- Preoperative haemoglobin
- Preoperative creatinine
- Height
- Weight
- NHS number, Date of Birth and Full Name for registry linkage (UK only)
- Residential postcode for registry linkage (UK only)
- Quality of life according to EQ-5D-3L (UK only)

Data collected during trial intervention period

Surgery & Anaesthesia

- Start and end times of anaesthesia
- Surgical procedure performed
- Open or laparoscopic procedure
- Anaesthetic technique
- Endotracheal tube removed at end of surgery
- Cardiac output monitor use
- Hours spent in post-anaesthetic care unit (recovery room)
- Actual level of care on the first night after surgery

Fluids

- Volume and type of intra-venous colloid solution during surgery
- Volume and type of intra-venous colloid solution during four hours after surgery
- Volume and type of intra-venous crystalloid solution during surgery
- Volume and type of IV crystalloid solution during four hours after surgery
- Volume of red blood cell and blood products during surgery

Drugs

- Use and type of inotrope (including start date/time and end date/time)
- Inotrope rate, infusion site
- Other drugs

Research Staff

- Additional staff present to deliver intervention during surgery
- Additional staff present to deliver intervention during four hours after surgery

Follow-up data

- 30 day post-operative infection (≥Clavien-Dindo grade II: see Appendix 1)
- 24 hour and 30 day adverse cardiac events (≥Clavien-Dindo grade II)
- 30 day acute kidney injury (≥Clavien-Dindo grade II)
- Other 30 day postoperative complications (≥Clavien-Dindo grade II)
- Red blood cell transfusion within 30 days after randomisation
- Parenteral nutrition within 30 days after randomisation
- Endoscopic or radiological intervention within 30 days after randomisation
- Repeat surgery within 30 days after randomisation (with indication)
- Unplanned critical care admission to treat complication(s) within 30 days after randomisation
- Planned critical care admission prolonged due to complication(s) within 30 days after randomisation
- Invasive mechanical ventilation after leaving operating room, within 30 days after randomisation
- Date of death (where applicable)
- Duration of hospital stay
- Number of days in level 2 and level 3 critical care within 30 days after randomisation
- Did the patient survive to discharge of primary hospital admission
- Re-admission to hospital within 30 days of randomisation
- Post-operative SARS-CoV-2
- Self-assessment of blinding of investigator that collected follow-up data
- Quality of life according to EQ-5D-3L health status measure (30 days)
- Quality of life according to EQ-5D-3L health status measure (180 days)

7.8 Predefined protocol deviations

• Failure to use cardiac output monitoring in an intervention group patient

- Failure to administer inotrope to an intervention group patient
- Administration of incorrect dose of inotrope to an intervention group patient
- Use of cardiac output monitoring in a control group patient

7.9 Follow-up procedures

To minimise bias, follow-up data will be collected by an investigator who is unaware of the study group allocation. Investigators will review a participant's medical record and contact participants by telephone to conduct brief interviews at 30 and 180 days after surgery. To collect data on secondary outcomes and facilitate the health economic analysis, we will request hospital episode statistics and mortality data from NHS Digital (formerly HSCIC) for participants in England or equivalent national database. Prospective consent for ONS/HES (or equivalent national database) data linkage will be sought before enrolment into the trial.

7.10 Withdrawal of participants

All study participants are free to withdraw from the study at any time. All randomised patients with a recorded outcome will be included in the final analysis on an intention to treat basis, unless a participant specifically asks for their data not to be included.

7.11 Self-assessment of blinding by research staff

Research staff collecting outcomes data will complete a self-assessment to allow us to report the effectiveness of blinding procedures during the trial. They will grade themselves as one of the following options:

- Suitably blinded
- May have known study group allocation
- Definitely knew study group allocation

7.12 End of study definition

The end of the study is defined as the point when the last patient has completed 180day follow-up. The Data Monitoring and Ethics Committee (DMEC) will monitor safety data throughout the trial, and will routinely meet to assess safety analyses. Based on these results, they could recommend termination of the trial on safety grounds. They will report any concerns to the Trial Steering Committee (TSC), who will inform the Sponsor and take appropriate action, which may include stopping the trial, to address concerns about participant safety. The Research Ethics Committee will be informed in writing if the trial is suspended or terminated early.

7.13 Schedule of assessment

Event/Visit	Screening	Before surgery	24 hrs after surgery	Hospital discharge	30 days after surgery	180 days after surgery
Inclusion/exclusion criteria	x					
Informed consent	x					
Demographic information		х				
Medical history		х				
Height and weight		х				
EQ-5D-3L (UK Only)		х			х	х
Randomisation		х				
Intraoperative information			х			
Fluid and inotropic therapy			х			
Review of medical notes			х	х	х	
Days of ICU and hospital				х		
Telephone contact					х	х
AE/SAE			х	х	х	х
End of trial form						Х

8. STATISTICAL CONSIDERATIONS

8.1 Sample size calculation

In order to detect a 5% absolute reduction (from 30% to 25%) for the primary outcome of postoperative infection up to 30 days (a risk ratio of 0.83), with 80% power, and an overall type I error rate of 5%, we require 2502 patients (1251 per arm). This sample size would also allow us to detect an absolute reduction in the primary outcome of 6% (from 30% to 24%) with 92% power.

8.2 Statistical analysis

Analyses will be performed according to intention-to-treat; all patients with a recorded outcome will be included in the analysis, and analysed according to the treatment to which they were randomised (13). Summary statistics by group, treatment effects, 95% confidence intervals, and p-values will be presented for primary and secondary outcomes, and process measures. Baseline and all other follow up data for the two groups will be summarised by treatment group, but not subjected to statistical testing.

The primary outcome of postoperative infection within 30 days from randomisation will be analysed using a mixed-effects logistic regression model with a random intercept for country (14). The model will adjust for surgical procedure category, age, gender, ASA grade, baseline haemoglobin, and baseline creatinine. ASA grade and procedure category will be included as categorical variables. The categories for ASA grade are II, III, and IV. The categories for procedure are (a) resection of colon, rectum or small bowel; (b) resection of pancreas and bowel; (c) resection of stomach

(non-obesity surgery); (d) resection of oesophagus (non-obesity surgery); (e) obesity surgery; (f) other surgery involving gut resection. Age, baseline haemoglobin, and baseline creatinine will be adjusted for using restricted cubic splines with three knots, and knot locations based on Harell's recommendations (15, 16). Missing baseline data will be accounted for using mean imputation (17). P-values <0.05 will be considered statistically significant. A statistical analysis plan will be written prior to data analysis taking place and any member of the trial team having access to unblinded data.

8.3 Health economic analysis

The health economic analysis will compare the incremental cost per quality adjusted life year (QALY) of cardiac output guided haemodynamic therapy for the prevention of postoperative morbidity compared to usual practice. Cost per patient in the intervention and usual care arms will be assessed from the perspective of the NHS. Costs and outcomes will be evaluated over the 180 day horizon of the trial and no discounting will be applied due to the short length of follow-up. The analysis will include the cost of the intervention in addition to the cost of healthcare resources consumed by patients over the 180 day period. The cost of cardiac output monitoring in the intervention arm will be obtained from trial centres. Data on the length of stay during the index admission will be used to estimate the cost of the initial inpatient episode. The cost of subsequent re-admissions to hospital during the 180 day period will be estimated using electronic health records obtained from the NHS Digital Hospital Episode Statistics (HES) database (18). Data obtained from trial centres and HES, including clinical casemix codes (HRG and OPCS-4) and length of stay, will be combined with the NHS Reference Costs inpatient schedule to estimate the cost per episode (19). Inpatient stays in critical care will be costed according to the level of care received using NHS Reference Costs adult intensive care schedule. Outcomes in the cost-effectiveness analysis will be measured in terms of QALY gained estimated using self-reported Euro-QOL 5-dimension (EQ-5D-3L) score collected at baseline, 30 days and 180 days in combination with UK population utility weights (20). QALYs will be calculated using the area under the curve (AUC) approach, taking into account the length of time spent alive during the follow-up period calculated using linked mortality data from the ONS. An assessment of missing data will be performed on the original cost and outcome data. The approach to handling missing data will depend on whether the data are missing due to incomplete followup or informative censoring. Appropriate statistical techniques will be applied to fill in missing fields where data are assumed to be missing at random (MAR). The strategy

for handling missing data in the economic analysis will be pre-specified in the health economic analysis plan prior to obtaining the dataset.

The analysis will gauge the additional cost per QALY gained in the intervention arm compared to usual care using an incremental cost-effectiveness ratio (ICER). Although random allocation to treatment group is designed to remove systematic differences in patient characteristics between groups, chance differences in baseline covariates may impact on the endpoints of the economic analysis. Baseline covariate adjustment will be performed by fitting regression models for mean cost and QALYs gained per patient (21). A generalised linear model with a log link and gamma distribution to control for positive skew will be used to estimate mean cost and linear multivariate regression will be used to estimate mean QALYs gained at 180 days follow-up. Cost and QALY gain will be modelled as a function of treatment assignment (as a dummy variable), age, sex, baseline secondary care cost based on inpatient episodes in the 3 months prior to the intervention obtained from HES, baseline EQ-5D-3L scores, ASA grade, haemoglobin and creatinine measured at baseline. Incremental cost and outcome adjusted for baseline differences in covariates between trial arms corresponds to the coefficient on the treatment dummy variable in the regression models.

The estimation of a confidence interval for the ICER statistic can be problematic for the following reasons: i) differences in QALYs between treatment arms tend to be very small, meaning that the denominator in the ratio may be zero or very close to zero, leading to an undefined value for the ICER; ii) high levels of skew due to a tendency for outliers and zero values in patient-level cost data; iii) costs and outcomes cannot be assumed to be uncorrelated. Non-parametric bootstrapping with replacement based on the observed data is an accepted approach to estimating confidence intervals for the ICER (22). The bootstrapping process will be carried out with 5000 iterations based on the original cost and outcome data using Stata/IC to achieve stability for interval estimates. Regression models will adjust for covariate imbalances on each bootstrapped re-sample. Adjusted incremental cost and outcome estimates will then be used to construct the mean and 95% confidence interval for the ICER. The distribution of incremental estimates will be plotted on a cost-effectiveness plane. A cost-effectiveness acceptability curve (CEAC) will plot the probability of cost-effectiveness of the intervention as a function of willingness-to-pay values per additional QALY gained in order to place the intervention in the context of

current acceptable willingness-to-pay levels for new healthcare technology according to the National Institute for Health and Care Excellence (NICE) (23).

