5.6 Health economic endpoints (UK only)

- Mean cost from the perspective of NHS at 180 days post-randomisation
- Quality Adjusted Life Years (QALY) at 180 days post-randomisation
- Incremental cost-effectiveness ratio

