7.3 Randomisation

Randomisation will occur after the participant has provided informed consent and shortly before the surgical procedure is due to start. Participants will be centrally allocated to treatment groups in a 1:1 ratio by minimisation with a random component. Minimisation variables will be country, surgical procedure category, and ASA grade. The surgical procedure categories are: resection of colon, rectum or small bowel; resection of pancreas and bowel; resection of stomach (non-obesity surgery); resection of oesophagus (non-obesity surgery); obesity surgery; other surgery involving gut resection. The ASA grades are: II, III, and IV. Each participant will be allocated with 80% probability to the group that minimises the between group differences in these factors among all participants recruited to the trial to date, and to the alternative group with 20% probability. To enter a patient into the OPTIMISE II trial, research staff at the site will log on to a secure web-based randomisation and data entry platform hosted by Queen Mary University of London and complete the patient's details to obtain a unique patient identification number and allocation to a treatment group. A patient's treatment group allocation will only be revealed to the

person performing randomisation.

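### The cost and QALY models omit surgical procedure category, the one minimisation factor that varies in the UK-only analysis and goes unadjusted: a minor loss of precision that is nearly free to avoid

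*Protocol*

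**What the plan says.** Section 7.3 of the protocol sets the allocation: "Minimisation variables will be country, surgical procedure category, and ASA grade". Balance is sought over the whole trial, not within country: "Each participant will be allocated with 80% probability to the group that minimises the between group differences in these factors among all participants".

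Section 8.2 carries procedure into the primary analysis: "The model will adjust for surgical procedure category, age, gender, ASA grade, baseline haemoglobin, and baseline creatinine", with country as a random intercept.

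Section 8.3 gives the economic covariates by name. The list opens "Cost and QALY gain will be modelled as a function of treatment assignment (as a dummy variable), age, sex, baseline secondary care cost" and closes with "baseline EQ-5D-3L scores, ASA grade, haemoglobin and creatinine measured at baseline". Procedure category is not in it, and no reason is given. Costs are modelled as follows: "A generalised linear model with a log link and gamma distribution to control for positive skew will be used to estimate mean cost". QALYs use linear regression. Intervals come from 5000 bootstrap re-samples of patients, with the same regressions refitted each time and no stratification stated.

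Section 5.6 restricts the economic endpoints to the UK. Section 7.7 lists the planned procedure category among the data recorded at randomisation.

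**The concern.** A factor used to balance allocation should normally be in the analysis model. If it predicts the outcome and is left out, the variation it explains stays in the residual. Where minimisation has balanced the factor, that variation does not contribute to the real sampling error of the treatment contrast, so the reported standard error is too large. Where it has not, the imbalance feeds into the estimate uncorrected.

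Of the three minimisation factors, ASA grade is in the economic models and country is constant among UK patients. Procedure is the only one that varies and goes unadjusted. It is also plausibly related to cost, because data "including clinical casemix codes (HRG and OPCS-4) and length of stay, will be combined with the NHS Reference Costs inpatient schedule" to price each episode, and OPCS-4 codes describe procedures. Section 8.3 itself justifies adjustment by the possibility of chance baseline differences, and that reasoning applies to procedure mix.

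At stake are the width of the intervals for incremental cost, QALYs and the ICER, and the steepness of the acceptability curve.

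**Working it through.** The protocol states no numerical figure for the precision of the economic analysis, so there is none to reproduce.

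**Inputs from the protocol.** 2502 patients (8.1); 1:1 minimisation with 80% probability on country, procedure (six categories) and ASA grade (three grades) over all participants (7.3); gamma log-link model for cost and linear model for QALYs, without procedure (8.3); UK patients only (5.6).

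**Assumptions, not in the protocol.** R², the share of outcome variance explained by procedure: 2% to 30%. UK share of patients: 30%, 60% or 100%. The mixes of country, procedure and ASA grade are also assumed.

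**Step 1: closed form, linear model, procedure fully balanced in the analysed patients.** Reported SE / true SE = 1/√(1−R²). True coverage of a nominal 95% interval = 2Φ(1.96/√(1−R²)) − 1. For example, at R² = 20%, 1/√0.80 = 1.118.

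| R² | SE ratio | True coverage |
|---|---|---|
| 2% | 1.01 | 95.2% |
| 5% | 1.03 | 95.6% |
| 10% | 1.05 | 96.1% |
| 20% | 1.12 | 97.2% |
| 30% | 1.20 | 98.1% |

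**Step 2: simulation of trial-wide minimisation, analysing the UK subset.** There were 800 runs per setting, with ASA grade adjusted in every model. For the gamma outcome, the procedure effect had SD 0.8√R² on the log scale and the dispersion was 0.64(1−R²), so R² there is a label for strength rather than an exact variance share. All columns except the last two describe the model without procedure. The last two columns divide the value without procedure by the value with it.

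| UK share | R² | Model | Reported / true SE | Type I error | True SD ratio | Reported SE ratio |
|---|---|---|---|---|---|---|
| 100% | 10% | linear | 1.09 | 3.2% | 0.0368/0.0368 = 1.00 | 1.05 |
| 100% | 30% | linear | 1.21 | 1.4% | 0.0331/0.0330 = 1.00 | 1.20 |
| 100% | 10% | gamma | 1.06 | 4.2% | 0.0317/0.0305 = 1.04 | 1.10 |
| 100% | 30% | gamma | 1.20 | 1.8% | 0.0303/0.0268 = 1.13 | 1.36 |
| 60% | 10% | linear | 1.09 | 3.2% | 0.0474/0.0468 = 1.01 | 1.05 |
| 60% | 30% | linear | 1.09 | 3.0% | 0.0476/0.0433 = 1.10 | 1.20 |
| 60% | 10% | gamma | 1.03 | 3.9% | 0.0420/0.0397 = 1.06 | 1.10 |
| 60% | 30% | gamma | 1.12 | 2.5% | 0.0417/0.0339 = 1.23 | 1.36 |
| 30% | 10% | linear | 1.01 | 5.4% | 0.0722/0.0700 = 1.03 | 1.05 |
| 30% | 30% | linear | 1.04 | 4.2% | 0.0707/0.0623 = 1.13 | 1.19 |
| 30% | 10% | gamma | 0.98 | 5.6% | 0.0620/0.0570 = 1.09 | 1.10 |
| 30% | 30% | gamma | 1.04 | 4.2% | 0.0634/0.0497 = 1.28 | 1.36 |

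Monte Carlo error is about 1/√(2×800) = 2.5% on an empirical SD and √(0.05×0.95/800) = 0.8 percentage points on a 5% error rate, so small differences between rows should not be read. With procedure included, type I error ran from 3.9% to 6.9%; the highest values were for the gamma model at a 30% UK share with model-based standard errors.

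The last two columns separate two mechanisms. At a 100% UK share in the linear model, the estimator itself is no more variable without procedure, and the excess is purely in the reported SE. At a 30% share the reported SE is roughly right, and the extra width is real variability from uncorrected imbalance.

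**Step 3: does the bootstrap cure it?** 150 simulated trials of 1200 patients in one country, R² = 30%, linear model, 150 patient-level re-samples each. Bootstrap SE / true SE was 0.0567/0.0495 = 1.15 without procedure and 0.0476/0.0491 = 0.97 with it. Re-sampling patients does not preserve the balance that minimisation produced, so the omission passes through to the intervals.

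**The case against.** A reader might infer that the economic standard errors ignore the randomisation and are too wide as a matter of fact. The protocol does not support that. ASA grade is adjusted for and country cannot vary within the UK, so one factor is missing rather than the whole scheme. Minimisation works across all participants, so procedure need not be balanced within the UK. At a 30% UK share, type I error without procedure was 4.2% to 5.6%, about nominal. Clear overstatement appears only when the UK share is high and procedure explains much of the variance. The protocol does not give the UK share.

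Nor does the protocol say that procedure is the main driver of cost. Costing by casemix code, length of stay and level of critical care makes a link plausible but does not size it. Nothing supports a material effect on QALYs. At R² of 2% to 5% the excess is 1% to 3%, which is negligible.

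It can also be said that section 8.4 promises a plan for each secondary study, including the economic analysis, and that 8.3 mentions a health economic analysis plan. A later plan could add the covariate. This softens the point without removing it: 8.3 leaves only the missing-data strategy to that plan and already states the covariates, so a plan that follows the protocol inherits the gap.

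Finally, the two harms trade off. The more imbalance there is within the UK, the nearer the unadjusted standard error is to valid. They should not be added together at full size. The reported standard error was nevertheless wider without procedure in every setting examined.

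**Conclusion.** The omission is real and unexplained, and it is inconsistent with the trial's own allocation scheme and primary model. The dependable consequence is a wider reported standard error for incremental cost, and possibly for QALYs, with chance imbalance in UK procedure mix uncorrected. In the simulations, the reported SE without procedure exceeded that with it by factors of 1.05 to 1.20 (linear) and 1.10 to 1.36 (gamma) at R² of 10% to 30%. Conservative intervals and a flatter acceptability curve are a further possibility, conditional on a large UK share.

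Both R² and the UK share are assumptions, and at low R² the effect is trivial. Any miscalibration from the omission is conservative: it adds no false-positive risk and does not touch the primary outcome. The severity is minor.

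**What to change.** In section 8.3, add planned surgical procedure category, as entered at randomisation, as a categorical covariate in both the cost and the QALY model, refitted in every bootstrap re-sample. Use the planned category, not the procedure performed, because the latter is recorded after allocation. State before unblinding how sparse UK categories will be merged, so that the models can be fitted in all re-samples. If procedure is to stay out, give the reason.

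The cost is one covariate and one merging rule. The data are already collected (7.7). With identity and log links and no treatment interaction, adding a balanced baseline covariate leaves the treatment effect being estimated unchanged. The only practical burden is handling rare categories.

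### The treatment coefficient of the log-link cost model is a log ratio of mean costs, not the incremental cost that the ICER, the plane and the CEAC need

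*Protocol*

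**What the plan says.** Protocol section 8.3 specifies two regression models.

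- **Cost:** "A generalised linear model with a log link and gamma distribution to control for positive skew will be used to estimate mean cost".
- **QALYs:** "linear multivariate regression will be used to estimate mean QALYs gained at 180 days follow-up".

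Both include treatment as a 0/1 term: "Cost and QALY gain will be modelled as a function of treatment assignment (as a dummy variable), age, sex", followed by further baseline covariates. One sentence then defines both increments, in cost and in outcome: each, "adjusted for baseline differences in covariates between trial arms corresponds to the coefficient on the treatment dummy variable in the regression models".

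The models are refitted in each of 5000 bootstrap re-samples, and the results feed three outputs:

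- **ICER:** "Adjusted incremental cost and outcome estimates will then be used to construct the mean and 95% confidence interval for the ICER".
- **Plane:** "The distribution of incremental estimates will be plotted on a cost-effectiveness plane".
- **CEAC:** the curve "will plot the probability of cost-effectiveness of the intervention as a function of willingness-to-pay values per additional QALY gained".

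The ICER is one of the UK health economic endpoints listed in section 5.6. Section 8.3 describes it as extra cost per QALY gained, so its numerator must be money.

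**The concern.** The defining sentence covers cost as well as outcome and refers to both models, so it applies to the log-link cost model. There the treatment coefficient is the log of a ratio of means. It has no currency unit and, for any plausible cost effect, lies close to zero.

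Willingness-to-pay thresholds run to thousands of pounds per QALY. If a number such as 0.05 stands where several hundred pounds should stand, net benefit is decided almost entirely by the sign of the QALY difference. The CEAC would then be nearly flat over any realistic threshold and would show little more than the probability that the QALY difference is positive. The cost axis of the plane, and the ICER with its confidence interval, would not be in pounds.

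**Working it through.** **Algebra.** With treatment T, covariates X and a log link:

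log E[cost] = a + bT + cX

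- Coefficient: b = log(mean cost under T=1 / mean cost under T=0), at given X.
- Adjusted incremental cost: the average over patients of exp(a + cX) × (exp(b) − 1). With M the average predicted cost under usual care and r = exp(b), this equals M(r − 1).

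For the linear QALY model, E[QALY] = a + bT + cX, so b is itself the adjusted difference. The protocol's rule is right there and wrong for cost. This result needs no numerical input.

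**Inputs for the size.** The protocol gives no mean cost, cost ratio, QALY difference or threshold value. All of the following are assumptions: M from 5,000 to 20,000 pounds, r from 0.95 to 1.10, QALY gain 0.01, threshold 20,000 pounds per QALY.

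**One case in full** (M = 10,000, r = 1.05):

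- Coefficient: ln(1.05) = 0.0488. Incremental cost: 10,000 × 0.05 = 500 pounds.
- ICER by the written rule: 0.0488 / 0.01 = 4.88. In money: 500 / 0.01 = 50,000 pounds per QALY.
- Net benefit by the written rule: 20,000 × 0.01 − 0.0488 = 199.95. In money: 200 − 500 = −300 pounds.

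**Range.** Net benefit at 20,000 pounds per QALY with a QALY gain of 0.01:

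| Cost ratio r | Coefficient ln(r) | Written rule, any M | Money, M = 5,000 | Money, M = 10,000 | Money, M = 15,000 | Money, M = 20,000 |
|---|---|---|---|---|---|---|
| 0.95 | −0.0513 | 200.05 | 450 | 700 | 950 | 1,200 |
| 1.02 | 0.0198 | 199.98 | 100 | 0 | −100 | −200 |
| 1.05 | 0.0488 | 199.95 | −50 | −300 | −550 | −800 |
| 1.10 | 0.0953 | 199.90 | −300 | −800 | −1,300 | −1,800 |

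The written rule gives 199.90 to 200.05 throughout. The value in money runs from +1,200 to −1,800 pounds.

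**Check on fitted models.** A gamma GLM with log link was fitted to simulated costs (20,000 patients, one covariate, control mean about 10,000 pounds). With a true ratio of 1.05 the coefficient was 0.0463 and the difference in average predicted cost 479 pounds. With a true ratio of 0.95 they were −0.054 and −536 pounds.

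**Effect on the CEAC.** Assume an incremental cost of +600 pounds (SE 569) and a QALY gain of 0.003 (SE 0.0063), both normal and uncorrelated.

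- In money at 20,000: mean net benefit 20,000 × 0.003 − 600 = −540; SE = √(126² + 569²) = 583; probability cost-effective Φ(−540/583) = 0.18.
- In money at 30,000: mean 90 − 600 = −510; SE = √(189² + 569²) = 600; probability 0.20.
- By the written rule the cost term is negligible at either threshold: Φ(0.003/0.0063) = 0.68.

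The direction of the assumed cost effect matters. With a saving of 500 pounds and the same SEs, mean net benefit at 20,000 is 60 + 500 = 560 and the probability in money is Φ(560/583) = 0.83, again against 0.68 by the written rule.

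**The case against.** The strongest reply is that the literal reading will not happen. The protocol's intent is plainly monetary: mean NHS cost is an endpoint in section 5.6, and section 8.3 speaks of cost per QALY. The wording that equates increments with coefficients is loose, and the bootstrap text refers to adjusted incremental estimates, not to coefficients. An ICER of about 5 per QALY would be noticed at first output. Section 8.3 also refers to a health economic analysis plan for missing data, and section 8.4 promises an analysis plan for each secondary study, including the health economic analysis. The correct post-estimation step could be written there.

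Part of this stands. Silent propagation into a published result is not certain. The sign of the cost difference is preserved, so points on the plane stay in the right quadrant. The primary, clinical secondary and safety outcomes are untouched. The money figures rest on assumed costs and standard errors, and the gap on the CEAC depends on the scenario.

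It does not rescue the sentence. The monetary intent shows that the rule contradicts the protocol's own aim. A later plan can fill a gap, but here the protocol fixes a definite rule, and a plan that followed it would inherit the error. Section 8.3 mentions no back-transformation, marginal effect or difference in predicted means. Exponentiating the coefficient would still give a ratio, not pounds. An analyst who does the right thing has to depart from the text, and the method then used would not be pre-specified.

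**Conclusion.** The concern holds. Section 8.3 defines incremental cost by a quantity that, under the specified log link, is a log ratio of mean costs. This follows from the model alone and depends on no assumed figure. Taken literally, it makes the ICER and its interval, the cost axis of the plane and the CEAC uninterpretable in pounds, and removes cost from the decision. Under the assumed inputs the net-benefit decision reverses in several cases (for example +199.95 against −300), and the probability of cost-effectiveness at 20,000 pounds per QALY moves from 0.18 to 0.68 in one scenario and from 0.83 to 0.68 in another. The effect is confined to the UK health economic endpoints. It should be corrected before the economic analysis is run.

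**What to change.** Replace the sentence in section 8.3, and carry the replacement into the health economic analysis plan, with a separate definition for each model:

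- **Incremental cost:** from the fitted gamma/log-link model, predict each patient's cost with treatment set to intervention and again with treatment set to usual care, keeping the other covariates as observed. The incremental cost is the average of the differences.
- **Incremental QALYs:** the treatment coefficient of the linear model, as now.
- **Bootstrap:** refit both models and recompute both quantities in each of the 5000 re-samples. Use these pairs for the ICER interval, the plane and the CEAC.

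An identity link for cost would also make the coefficient a difference in pounds, but that changes the model and is optional.

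The cost is one sentence of text and one post-estimation step per fit. No data collection, sample size or clinical analysis changes.
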